### 5.2.6. Definition of Start of New Anticancer Therapy

Start date of new anticancer therapy (drug, radiation with curative intent) is used to determine the end of the on-treatment period (see [Section 3.5](#)) and for censoring in efficacy analyses (see [Section 6.1](#)).

The start date of new anticancer therapy is the earliest date after first dose date amongst the following:

- Start date of anticancer drug therapy recorded in the ‘Concomitant Treatment’ eCRF pages with category = “Follow-up Cancer Therapy”.
- Start date of radiation therapy recorded in ‘Radiation Treatment’ and ‘Non-drug Treatments (NXT RAD)’ eCRF pages.

When start date of anticancer therapy is missing or partially missing, the imputation rules described in [Section 5.3.3.4](#) should be applied using the data collected on the eCRF pages described above.

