### 3.5. Safety Endpoints

Safety endpoints will be summarized based on the on-treatment period unless otherwise specified.

On-treatment period is defined as the time from the first dose of study intervention through the minimum of [28 days after last dose, (start day of new anticancer therapy – 1 day)]. Anticancer therapy includes drug therapy and radiation with curative intent; the start of new anticancer therapy after the first dose of study intervention is derived as outlined in [Section 5.2.6](#). Adverse events occurring on the same day as the first dose of study intervention will be considered to have occurred during the on-treatment period. All other assessments which occur on the same day as the first dose of study intervention will be considered baseline assessments (see [Section 3.4](#) for the definition of baseline).

Safety data collected after the on-treatment period as described above will be listed but not summarized.

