### 5.3.3.4. Date of Start of New Anticancer Therapy

Incomplete dates for start date of new anticancer therapy (drug therapy, radiation with curative intent) will be imputed as follows and will be used for determining censoring dates for efficacy analyses and in the derivation of the end of the on-treatment period. PD date below refers to PD date by investigator assessment. If the imputation results in an end date prior to the imputed start date, then the imputed start date should be set to the end date.

- The end date of new anticancer therapy will be included in the imputations for start date of new anticancer therapy. If the end date of new anticancer therapy is
  - completely missing then it will be ignored in the imputations below;
  - partially missing with only year (YYYY) available then the imputations below will consider 31DECYYYY as the end date of the new anticancer therapy;
  - partially missing with only month and year available then the imputations below will consider the last day of the month for MMMYYYY as the end date of the new anticancer therapy.
- For participants who have not discontinued study intervention at the analysis cutoff date, last dose of study intervention is set to the analysis cutoff date in the imputations below.

- If the start date of new anticancer therapy is completely or partially missing, then the imputed start date of new anticancer therapy is derived as follows:
  - Start date of new anticancer therapy is completely missing
    - Imputed start date = min [max(PD date + 1, last dose of study intervention + 1), end date of new anticancer therapy]
  - Only year (YYYY) for start of anticancer therapy is available
    - IF YYYY < Year of min [max(PD date + 1, last dose of study intervention + 1), end date of new anticancer therapy]
 

THEN imputed start date = 31DECYYYY;
    - ELSE IF YYYY = Year of min [max(PD date + 1, last dose of study intervention + 1), end date of new anticancer therapy]
 

THEN imputed start date = min [max(PD date + 1, last dose of study intervention + 1), end date of new anticancer therapy];
    - ELSE IF YYYY > Year of min [max(PD date + 1, last dose of study intervention + 1), end date of new anticancer therapy]
 

THEN imputed start date = 01JANYYYYY.
  - Both Year (YYYY) and Month (MMM) for start of anticancer therapy are available
    - IF YYYY = Year of min [max(PD date + 1, last dose of study intervention + 1), end date of new anticancer therapy], AND
 

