**Phase 2**

The primary endpoint in the Phase 2 part is ORR per IMWG response criteria, defined as the proportion of participants with an objective response per IMWG response criteria as determined by investigator.

Objective response is defined as having a best overall response (BOR) of confirmed stringent complete response (sCR), complete response (CR), very good partial response (VGPR) or partial response (PR).

For all efficacy endpoints per IMWG response criteria, BOR will be assessed based on reported overall responses recorded at evaluation time points from the date of first dose until

090177e1a0f4f44c\Approved\Approved On: 14-Jun-2024 22:12 (GMT)

the first documentation of confirmed PD, death or start of new anti-cancer therapy, whichever occurs first.

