### 6.2.2. Progression-free Survival

PFS is defined as the time from the date of first dose until confirmed PD per IMWG criteria as determined by investigator or death due to any cause, whichever occurs first. The rules for PD confirmation are described in [Table 4](#).

PFS will be calculated as follows:

$$\text{PFS (months)} = [\text{date of event or censoring} - \text{date of first dose} + 1] / 30.4375.$$

PFS will be censored as follows:

- For participants who do not have an event (confirmed PD per IMWG criteria or death due to any cause), censoring will occur on the date of the last adequate disease assessment;
- For participants who start a new anticancer therapy (as defined in [Section 5.2.6 in the master SAP](#)) prior to an event, censoring will occur on the date of the last adequate disease assessment before the new anticancer therapy;
- For participants with an event after a gap of 2 or more missing disease assessments, censoring will occur on the date of the last adequate disease assessment before the gap;
- Participants who do not have an adequate post-baseline disease assessment will be censored on the date of first dose of study intervention unless death occurs on or before the time of the second planned disease assessment (i.e.,  $\leq 70$  days after the date of first dose) in which case the death will be considered an event.

The censoring and event date options to be considered for the PFS analysis are presented in Table 5. Adequate post-baseline disease assessment is defined in [Section 5.2.10 in the master SAP](#).

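### Section 5.2.6 of the March 2021 SAP limits radiation to curative intent when it defines new anticancer therapy, but not when it derives the date

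*SAP*

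**What the plan says.** In the SAP dated 18 March 2021, Section 5.2.6 opens: "Start date of new anticancer therapy (drug, radiation with curative intent) is used to determine the end of the on-treatment period". The same sentence applies the date to censoring in the efficacy analyses and points to Section 6.1. Section 3.5 gives the same scope ("Anticancer therapy includes drug therapy and radiation with curative intent") and sends the reader to 5.2.6 for the derivation. Section 5.3.3.4 repeats it: "Incomplete dates for start date of new anticancer therapy (drug therapy, radiation with curative intent) will be imputed as follows".

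The derivation in 5.2.6 then reads: "The start date of new anticancer therapy is the earliest date after first dose date amongst the following". It has two bullets.

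- **Drug.** Taken from the Concomitant Treatment "eCRF pages with category" restricted to follow-up cancer therapy.
- **Radiation.** "Start date of radiation therapy recorded in" the Radiation Treatment and Non-drug Treatments (NXT RAD) eCRF pages. No intent condition is attached.

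The Sub-study A SAP (Section 3.1, Phase 2) ends the best-response window at confirmed PD, "death or start of new anti-cancer therapy, whichever occurs first". For participants who start a new therapy before an event, its PFS section (6.2.2) says "censoring will occur on the date of the last adequate disease assessment before the new anticancer therapy", and it cites Section 5.2.6 of the master SAP for the definition. The Sub-study B SAP (Section 6.2.3) has the same rule and citation.

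**The concern.** One section gives two rules for one variable. Under the definition, radiotherapy given for a purpose other than cure does not count as new anticancer therapy. Under the derivation it does, as soon as its start date is on either page. The drug bullet carries a filter, so the absence of one on the radiation bullet reads as a rule and not as shorthand.

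The variable is used widely. It bounds the primary response assessment, censors the time-to-event endpoints and closes the period in which adverse events count as treatment-emergent. In an open-label study with investigator-assessed response, the choice between the two rules should not be left to programming or settled after the data have been seen.

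**Working it through.** No arithmetic decides this. The check sets the statements side by side and traces the date to each place it is used.

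**1. Definition against derivation**

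| Place (SAP of 18 March 2021) | Radiation that counts |
|---|---|
| 3.5 | curative intent |
| 5.2.6, lead sentence | curative intent |
| 5.3.3.4, imputation | curative intent |
| 5.2.6, radiation bullet | any start date on two eCRF pages |

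Section 3.5 defers to 5.2.6 for the derivation. Section 5.2.6 also says that missing dates are imputed from the records on the pages it has just listed, so the imputation draws on the same unfiltered records. No section names an intent field or says how palliative radiotherapy is to be left out.

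**2. Where the date is used**

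- **Best overall response.** The window closes at new anticancer therapy (March 2021 SAP 3.1.2 and 6.1.2; Sub-study A 3.1 and 6.1.2; Sub-study B 3.2.1 and 6.2.1).
- **PFS.** Censored at the last adequate assessment before the new therapy (March 2021 SAP 6.2.2; Sub-study A 6.2.2; Sub-study B 6.2.3). This reason ranks first in the sub-study censoring hierarchies (Sub-study A Table 6; Sub-study B Table 4).
- **DOR and duration of complete response.** Both inherit the PFS rule (Sub-study A 6.2.3 and 6.2.4; Sub-study B 6.2.4 and 6.2.5).
- **MRD negativity.** The window closes on the same event in the sub-study SAPs (Sub-study A 6.2.7; Sub-study B 6.2.8). The March 2021 SAP (6.2.7) sets no such limit.
- **On-treatment period.** It ends at the earlier of 28 days after last dose and the day before new therapy (3.5). Later safety data appear in listings only.

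**3. When ORR changes**

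Let R be the start of non-curative radiotherapy and C the date of the assessment that confirms a first response of PR or better.

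- R after C: the objective response is already established and ORR is unchanged. The window still closes, so a later deepening to CR would not count.
- R before C: the confirming assessment falls outside the window. With a PR before R and nothing usable after it, Sub-study A Table 4, scenario 22, gives SD. A participant irradiated before any response is a non-responder under the estimand in Sub-study A 6.1.2.

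**4. The safety window**

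Let L be the date of last dose. Under the definition, with no curative radiation or other new therapy, the period ends at L + 28. Under the derivation it ends at R − 1 whenever that is earlier. The days lost are (L + 28) − (R − 1) = L − R + 29. Events starting in those days would not be treatment-emergent, even for a participant still receiving study drug.

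**5. The plan's design figures**

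Recalculation agrees with the plan. With the Beta(1.3, 0.7) prior, 38/50 gives a Beta(39.3, 12.7) posterior with median 75.9% and 90% credible interval 65.3% to 84.7%. The two-stage design at a true ORR of 80% gives 0.806 for GO and 0.047 for a futility stop. None of these depends on the radiation wording, and none changes with the fix.

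**The case against.** **The March 2021 text may not be the master SAP in force.** The Sub-study A SAP lists 18 March 2021 as its own version 1. Several master-SAP references in the sub-study SAPs do not fit this document: baseline summaries are cited at 6.5.1 but stand at 6.6.1, and safety is cited at 6.6 but stands at 6.7. Sub-study B has a 42-day DLT period and cites a Section 4 that here fixes 35 days. A separate or later master SAP may exist. Even so, the references to 5.2.6 match this section in number and topic, and no other text of it is available. The doubt is a reason to carry the correction into whichever master SAP applies; it does not remove the contradiction.

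**The definition is stated three times, so a careful programmer would apply it.** That is possible. But Section 3.5 points to the list as the derivation, and the list gives no means of applying the qualifier.

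**The scenario may not arise.** This stands as a limit on size. The documents do not show that the two pages capture palliative radiotherapy during the study. Whether it is permitted is left to the sub-study protocols (protocol Section 6.8), which are not supplied. Protocol Section 8.1.3 mentions irradiated plasmacytomas without saying when the irradiation takes place.

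**Conclusion.** The contradiction is in the text and should be removed. If the bullets are programmed as listed, non-curative radiotherapy recorded on those pages would censor PFS, DOR and duration of complete response, close the best-response and sub-study MRD windows, and shorten the on-treatment safety period. This rests on two assumptions: that the list is followed literally, and that the pages hold such records.

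The size is unknown. A reader might assume a rate of palliative radiotherapy, turn it into a number of mis-handled participants among the 50 in Phase 2, and set that against a margin of one responder: the posterior probability that ORR is at least 65% is 0.955 at 38/50 and 0.916 at 37/50. The documents do not support that inference, for three reasons.

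- They give no rate.
- Only radiotherapy before confirmation, in someone who would have gone on to a confirmed response, lowers the count. Mis-handled participants are not the same as lost responders.
- 38/50 is not binding. Sub-study A Section 5.1.2.2 says that reaching the critical number may suffice for further development without being required, and that key secondary endpoints also count. Sub-study B has no ORR decision rule.

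No number of affected participants or lost responders should be claimed.

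**What to change.** Make the derivation match the definition. In the radiation bullet of Section 5.2.6, add the curative-intent condition and name the eCRF field that records intent. If intent is not collected, specify a documented review of radiotherapy records, completed before database lock and carried out without using response outcomes.

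If the sponsor means all radiation to count, remove the curative-intent qualifier from Sections 3.5, 5.2.6 and 5.3.3.4 instead. Either way, state one rule and carry it into whichever master SAP the sub-study SAPs cite.

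The cost is one qualifier and one program filter, plus a record review if intent is not collected. Sample size, futility boundary and operating characteristics stay as they are.

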### 5.2.7. Date of Last Contact

The date of last contact will be derived for participants not known to have died at the data cutoff date using the latest complete date (ie, imputed dates will not be used in the derivation) among the following:

- All assessment dates (eg, blood draws [laboratory, Pharmacokinetics (PK)], vital signs, physical exam, performance status, ECG, Echocardiograms [ECHO]/multigated acquisition [MUGA] scans, disease assessments);
- Start and stop dates of concomitant therapies including non-drug treatments or procedures;
- Completion dates for PRO Questionnaires;

- Start and end dates of new therapies administered after study intervention discontinuation including systemic therapy, radiation, and surgeries;
- AE start and end dates;
- Last date of contact collected on the ‘Survival Follow-up’ CRF (do not use date of survival follow-up assessment unless status is ‘alive’);
- Study intervention start and end dates;
- Date of discontinuation on disposition CRF pages (do not use if reason for discontinuation is lost to follow-up or death).

Only dates associated with actual examinations of the participant will be used in the derivation. Dates associated with a technical operation unrelated to participant status such as the date a blood sample was processed or dates when data were entered into the CRF will not be used. Assessment dates after the data cutoff date will not be applied to derive the last contact date.

#### **5.2.8. Disease Assessment Date**

The Date of Disease Assessment at each nominal timepoint as provided by the investigator on the IMWG response CRF page will be utilized for the respective analyses.

#### **5.2.9. Adequate Baseline Disease Assessment**

Adequate baseline is defined using the following criteria:

- All baseline disease assessments must be within 28 days prior to and including the date of first dose;
- All documented lesions must have non-missing assessments (ie, non-missing measurements for target lesions and meeting criteria for measurable lesions, and non-missing lesions status at baseline for non-target lesions);
- Baseline lesions must be assessed with an acceptable method of tumor assessment as specified in the protocol (eg, PET/CT, CT or MRI);
- Measurable disease based on IMWG criteria as defined by at least 1 of the following:
  - Serum M-protein >0.5 g/dL by SPEP;
  - Urinary M-protein excretion  $\geq 200$  mg/24 hours by UPEP;
  - Serum immunoglobulin FLC  $\geq 10$  mg/dL ( $\geq 100$  mg/L) AND abnormal serum immunoglobulin kappa to lambda FLC ratio (<0.26 or >1.65).

### 5.2.10. Adequate Post-baseline Disease Assessment

An adequate disease assessment is defined as an assessment where a time-point response of sCR, CR, VGPR, PR, minimal response (MR), Stable Disease (SD) or PD has been provided. Timepoints where the response is not evaluable or no assessment was performed will not be used for determining the censoring date for time-to-event endpoints including PFS, DOR and DOCCR.

### 5.2.11. Nominal and Unscheduled Visits

For all algorithms and analyses, visit labels as specified on the CRF will be used as the nominal timepoint (ie, assessment will not be slotted).

Unless otherwise specified, unscheduled assessments will not be displayed in summary tables by nominal visit/timepoint. Unscheduled assessments will be used when deriving baseline and worst case on-treatment for safety and PRO analyses (except where noted for baseline ECGs). Additionally, unscheduled assessments will be used for efficacy analyses (eg, defining date of progression/censoring, best overall response, date of last contact).

### 5.2.12. Standard Deviations and Reporting Conventions

The following conversion factors will be used to convert days into weeks, months or years: 1 week = 7 days, 1 month = 30.4375 days, 1 year = 365.25 days.

#### Demographics and physical measurements:

- Age [years]:
  - $(\text{date of given informed consent} - \text{date of birth} + 1) / 365.25$ ;
  - In case of missing day: Age [years]:  $(\text{year/month of given informed consent} - \text{year/month of birth})$ ;
  - In case only year of birth is given: Age [years]:  $(\text{year of given informed consent} - \text{year of birth})$ .

The integer part of the calculated age will be used for reporting purposes.

- Body mass index (BMI)  $(\text{kg}/\text{m}^2) = \text{weight} (\text{kg}) / [\text{height} (\text{m})]^2$ .

For reporting conventions, mean and median should generally be displayed 1 more decimal place than the raw data and standard deviation should be displayed to 2 more decimal places than the raw data. Percentages will be reported to 1 decimal place. The rounding will be performed to closest integer/first decimal using the common mid-point between the 2 consecutive values. For example, 5.1 to 5.4 will be rounded to an integer of 5, and 5.5 to 5.9 will be rounded to an integer of 6.

### 5.2.13. Analyses for Continuous and Qualitative Variables

Continuous variables will be summarized using descriptive statistics ie, number of non-missing values and number of missing values [ie, n (missing)], mean, median, standard deviation, minimum, maximum and first and third quartile (Q1 and Q3).

Qualitative variables will be summarized by frequency counts and percentages. Unless otherwise specified, the calculation of proportions will include the missing category. Therefore, counts of missing observations will be included in the denominator and presented as a separate category.

In case the analysis refers only to certain visits, percentages will be based on the number of participants still present in the study at that visit, unless otherwise specified.

### 5.2.14. Analyses for Time-to-Event Endpoints

Kaplan-Meier estimates (product-limit estimates) will be presented together with a summary of associated statistics including the median time with 2-sided 95% CIs. Probabilities of an event at particular timepoints will be estimated with corresponding 2-sided 95% CIs. The CI for the median will be calculated according to Brookmeyer and Crowley, 1982 and the CIs for the survival function estimates at particular timepoints will be derived using the log(-log) method.

## 5.3. Methods to Manage Missing Data

Unless otherwise specified, all data will be evaluated as observed, and no imputation method for missing values will be used.

Any imputations will occur at the analysis dataset level. Additionally, in all data listings imputed values will be presented and flagged as imputed.

Missing statistics, eg, when they cannot be calculated, should be presented as ‘ND’ for not done, ‘NR’ for not reached or ‘NA’ for not applicable. For example, if N=1, the measure of variability cannot be computed and should be presented as ‘ND’ or ‘NA’.

### 5.3.1. Missing Pharmacokinetic Data

#### Concentrations below the limit of quantification

For all calculations and figures, all concentrations assayed as below the limit of quantification (BLQ) will be set to zero. The BLQ values will be excluded from calculations of geometric means and their CIs. A statement similar to ‘All values reported as BLQ have been replaced with zero’ will be included as a footnote to the appropriate tables and figures. In listings BLQ values will be reported as below limit of quantification (“<LLOQ”), where LLOQ will be replaced with the corresponding value from the analytical assay used.

## Deviations, missing concentrations and anomalous values

In summary tables, concentrations will be set to missing if one of the following cases is true:

- A concentration has been reported as ND (ie, not done) or NS (ie, no sample);
- A deviation in sampling time is of sufficient concern or a concentration has been flagged as anomalous by the clinical pharmacologist.

At the discretion of the clinical pharmacologist, summary statistics may not be presented at a particular time point if more than 50% of the data are missing. For analysis of pharmacokinetic concentrations, no values will be imputed for missing data. If less than 3 evaluable concentrations or PK parameters at a given timepoint are available, only minimum and maximum will be presented.

### 5.3.2. Missing ECG Data

For QTc analyses, no values will be imputed for missing data. If 1 or 2 of the triplicate measurements for an ECG parameter are missed, the average of the remaining 2 measurements or the single measurement, respectively, can be used in the analyses. If all triplicate measurements are missing at a timepoint for an ECG parameter, no values will be imputed for this timepoint. If the triplicate needs to be repeated because of an artifact, then the repeated triplicate will be reported on an unscheduled CRF page. Based on a review of the data, these unscheduled assessments may be used in place of the assessments at the nominal time. Data review and consultation with the study team is required to flag these cases.

